STUDY OBJECTIVE(S)	
Primary objective:
 
 To collect 12 weeks of real-use (usability) data assessing the robustness and user interaction of the new alirocumab auto-injector device (which is referred to as SYDNEY), in unsupervised settings on Weeks 4, 8, and 12. 
Secondary objectives:
 
Device-related:
 
 To collect real-use (usability) data assessing the robustness and user interaction of SYDNEY and the current 1 mL alirocumab auto-injector device (which is referred to as AI) in supervised settings on Week 0 (Day1). 
Pharmacokinetics:
 
 To compare alirocumab pharmacokinetics (PK) 300 mg every 4 weeks (Q4W) administered using SYDNEY and AI, from baseline until Week 4. To evaluate alirocumab PK 300 mg Q4W administered using SYDNEY, until Week 16. 
Anti-drug antibodies:
 
 To evaluate the development of anti-drug (alirocumab) antibodies (ADA). 
Efficacy/pharmacodynamics:
 
 To compare the percent and absolute change in LDL-C from baseline to Week 4 using SYDNEY and AI. To evaluate the percent and absolute change in LDL-C from baseline to Weeks 8, 12 and 16, using SYDNEY. 
Safety:
 
 To evaluate the safety and tolerability of alirocumab 300 mg Q4W, using both SYDNEY and AI.
STUDY DESIGN	
This is a multicenter, randomized, open-label, 16-week study, with 2 parallel arms (parallel-arms period) for the first 4 weeks, and then only one arm (single-arm period) for the subsequent weeks until Week 16.
 
Patients will be randomized to receive self-administered alirocumab 300 mg Q4W via either SYDNEY or AI for the first injection on Week 0 (Day 1).

	
Subsequently, all patients will receive self-administered alirocumab 300 mg Q4W via SYDNEY for the 2nd, 3rd and 4th injections on Week 4 (Day 29), Week 8 (Day 57) and Week 12 (Day 85).


STUDY POPULATION Main selection criteria
	
Main Inclusion Criteria:
 
 • Patients are in either category A or B (below), and are not adequately controlled with a stable daily dose of atorvastatin (20 mg or 40 mg), or rosuvastatin (10 mg or 20 mg) for at least 4 weeks prior to the screening visit (Week -2), with or without other lipid-modifying therapy (LMT). A) Patients with heterozygous familial hypercholesterolemia (heFH)** **Diagnosis of heFH must be made either by genotyping or by clinical criteria. For those patients not genotyped, the clinical diagnosis may be based on either the WHO criteria/Dutch Lipid Clinical Network criteria with a score >8 points or the Simon Broome register diagnostic criteria with a criterion for definite FH. OR B) Non-FH patients at high or very high cardiovascular (CV) risk. High and very high cardiovascular risk patients include patients with coronary heart disease (CHD), non-CHD cardiovascular disease (CVD), and other risk factors. • Patient willing and able to self-inject for the duration of the study. • Signed Written Informed Consent Form. 
Key Exclusion Criteria:
 
 • LDL-C <70 mg/dL (<1.81 mmol/L) at the screening visit (Week-2). • Currently taking a daily dose of statin that is not atorvastatin 20 mg or 40 mg, or rosuvastatin 10 mg or 20 mg. • Not on a stable dose of LMT (including statin) for at least 4 weeks, prior to the screening visit (Week- 2) and from screening to randomization. • Having previously used any device for the proprotein convertase subtilisin/kexin type 9 (PCSK9) inhibitor administration, or having participated in any clinical trial for a PCSK9 inhibitor. • Fasting serum Triglyceride (TG) >400 mg/dL (>4.52 mmol/L) at the screening visit (Week-2).

Total expected number of patients
	
66 randomized patients :
 
 • A group of 33 patients using SYDNEY in the entire study treatment period, • A group of 33 patients using AI for the first 4 weeks (parallel-arms period), then switching to SYDNEY (during the single-arm period).

STUDY TREATMENT(s)
 
Investigational Medicinal Product A (new auto-injector device)
	
Alirocumab delivered via the new 2 mL auto-injector device (SYDNEY).


Formulation:
	
Sterile alirocumab drug product supplied at a concentration of 150 mg/mL in histidine (6 mM), polysorbate 20 (0.1 mg), sucrose (100 mg), and Water for Injection USP, to pH 6.0.

Route(s) of administration:
 
Dose regimen:
	
Subcutaneous (SC) in the abdomen or thigh (site of injection to be documented).
 
300 mg Q4W administered as 1 single injection of 2 mL.
 
Self-administration on:
 
 • Week 0 (Day 1), at the investigator site, supervised. • Week 4 (Day 29) and Week 8 (Day 57) at the investigator site, or at home , unsupervised. • Week 12 (Day 85) at the investigator site, observed only (also considered unsupervised).

Investigational Medicinal Product B (current auto-injector device)
 
Formulation:
 
Route(s) of administration:
 
Dose regimen:
	
Alirocumab delivered via the current (commercial) 1 mL auto-injector device (AI).
 
Sterile alirocumab drug product supplied at a concentration of 150 mg/mL in histidine (6 mM), polysorbate 20 (0.1 mg), sucrose (100 mg), and Water for Injection USP, to pH 6.0.
 
Subcutaneous (SC) in the abdomen or thigh (site of injection to be documented).
 
300 mg Q4W administered as 2 injections of 1 mL.
 
Self-administration on:
 
 • Week 0 (Day 1), at the investigator site, supervised.

ENDPOINT(S)
	
Primary endpoint:
 
Number (%) and types of SYDNEY-associated product technical complaints* (PTCs) at the unsupervised injections on Weeks 4, 8, and 12.
 
Secondary endpoints:
 
Device-related endpoints:
 
 • For both devices: 
 - Number (%) of patients with auto-injector associated PTCs (overall and by type) at the supervised injections (Week 0, Day 1). - Injection experience questionnaire. • For SYDNEY only: 
 - Number (%) of patients with a SYDNEY - associated PTC (overall and by type) at the unsupervised injections on Weeks 4, 8, and 12. - Patient perspective questionnaire. - Injection-Treatment Acceptance Questionnaire (I-TAQ[®]). 
Pharmacokinetics:
 
 • Alirocumab PK parameters after the first and the last dosing.

[figure not shown]
	
 Free and total PCSK9 levels measured using PK serum samples. 
Anti-drug antibodies:
 
 ADAs assessed throughout the study. 
Efficacy/pharmacodynamics:
 
 Percent and absolute change from baseline in LDL-C at Weeks 4, 8, 12 and 16. 
Safety:
 
 Adverse events (AEs), including Serious Adverse Events (SAEs) and Adverse events of special interest (AESIs), laboratory data, vital signs assessed throughout the study. 
*PTC Definition: All complaints that triggered an investigation by the Device Department will be categorized as device-related, patient-related, undetermined, or not related to device nor patient. In this study, a PTC is defined as any complaint reported on the Patient Complaint form that triggered an investigation by the Device Department and was categorized as either device-related, patient-related or undetermined, whether or not associated with an AE. Of note, the complaints categorized as not related to device nor patient will not be considered as a PTC. This definition will be used for both primary and secondary endpoints. * In case a PTC is associated with the occurrence of an AE, the AE must be documented on an AE page in the electronic case report form (e-CRF) and the PTC must be described. In case a PTC is associated with the occurrence of a SAE, the SAE must be reported to the Monitoring Team in accordance with the SAE reporting procedures.

ASSESSMENT SCHEDULE
	
The study will consist of the following visits:
 
 Visit 1 (between Week -2 and Week 0), screening visit, on-site visit. Visit 2 (Week 0, D1): randomization, baseline visit, on-site visit. Visits 3 through 11 (Week 1 through Week 15): 
 Visits 3, 4, 5, 9, 10, and 11: PK sampling will be collected at these visits. These visits may be performed on site or as home-visits. Visits 6 and 7 (Weeks 4 and 8): These visits may be performed on site or as home-visits. Visit 8 (Week 12): end-of-treatment (EOT) Visit, on site Visit 12 (Week 16): end-of-study (EOS) Visit, on site.

STATISTICAL CONSIDERATIONS
	
Sample size determination No formal sample size was calculated for this study: sample size is based on empirical considerations. Considering a drop-out rate of 10% it is proposed to randomize 66 patients overall (33 in each group) in order to ensure 60 evaluable patients overall (30 in each group) resulting in

	
180 unsupervised planned injections using SYDNEY. Patients in the AI group will switch to SYDNEY group at the time of the second injection; therefore, it will ensure to have 60 evaluable patients using SYDNEY for the 2nd, 3rd and 4th unsupervised injections.
 
With 60 evaluable patients using SYDNEY, a total of 180 unsupervised injections is expected to be achieved during the study. Expecting a maximum of 3 observed PTC over the 180 injections (observed PTC rate of 1.67%) with SYDNEY, the upper bound of the 2-sided 95% confidence interval (CI) calculated with the Wilson score method will be no higher than 5.2%.
 
Analysis population
 
The primary endpoint will be analyzed on the safety population of the single-arm period that will consist of all randomized patients who continue in the single-arm period (from Week 4, to Week 16), and receive at least 1 dose or part of a dose of Investigational Medicinal Product (IMP) during this period.
 
Analysis of the primary endpoint
 
The primary endpoint (ie, number (%) and type of SYDNEY-associated PTCs at the unsupervised injections) will be described on the safety population for the single-arm period. The number and % of PTCs will be provided with the 95% CI using Wilson score method. If applicable, the number of PTCs per patient will be described.
 
Analysis of secondary endpoints
 
All secondary device-related endpoints will be analyzed on the safety population using descriptive statistics. In addition, 95% CI for the number of PTCs, number and % of patients with any PTCs will be provided using Wilson score method.
 
Pharmacokinetics
 
PK parameters and levels of PCSK9 (total and free) will be summarized descriptively by auto-injector device group.
 
After the first administration only, for log-transformed maximum plasma concentration (C_{max}), area under the curve concentration versus time curve extrapolated to infinity (AUC_{0-tau}) and trough concentration (C_{trough}), the difference between auto-injector devices will be assessed using a linear fixed effects model.
 
Estimate and 90% CI for the ratio of geometric means (SYDNEY/current AI) will be computed for C_{max}, AUC_{0-tau} and C_{trough}.
 
Anti-drug antibodies
 
Results of ADA will be summarized by auto-injector device group using descriptive statistics.
 
Pharmacodynamics
 
Percent and absolute change from baseline in LDL-C will be summarized descriptively for each auto-injector device.
 
At Week 4 only, statistical analyses will compare auto-injector devices using an ANCOVA model to determine the estimates and 95% confidence intervals for the difference between means of percent LDL-C change for AI versus SYDNEY.

--	--

	
Safety and tolerability
 
The safety analysis will be based on the review of the individual data and descriptive statistics.
 
Adverse events will be classified using Medical Dictionary for Regulatory Activities (MedDRA) system organ class and preferred term. The number of treatment-emergent adverse events (TEAEs) will be tabulated by auto-injector device, as well as treatment-emergent AESIs (including in particular local injection site reactions LISR), treatment-emergent SAEs, TEAEs leading to permanent treatment discontinuation.
 
For vital signs and laboratory parameters, the number of patients with abnormalities and/or potentially clinically significant abnormalities (PCSAs) will be summarized by auto-injector device.

DURATION OF STUDY PERIOD (per patient)	
Total study duration (per patient) is expected to be up to 18 weeks:
 
• Up to 2 weeks of screening period• 16 weeks of study treatment period (auto-injector device assessment phase).

1 FLOW CHARTS

1.1 GRAPHICAL STUDY DESIGN

1.2 STUDY FLOW CHART

Phase	Screening	Treatment Phase										
Day ^a	D-14 to D-1	D1	D8 (±1)	D15 (±1)	D22 (±1)	D29 (±3)	D57 (±3)	D85 (±3) EOT	D92 (±1)	D99 (±1)	D106 (±1)	D113 (±3) EOS
Week	Wk-2 to Wk 0	Wk 0	Wk 1	Wk 2	Wk 3	Wk 4	Wk 8	Wk 12	Wk 13	Wk 14	Wk 15	Wk 16
Visit (visit number)	1	2	3 ^b	4 ^b	5 ^b	6 ^b	7 ^b	8	9 ^b	10 ^b	11 ^b	12
Place where visits may occur	On-site	On-site	On-site or home	On-site	On-site or home	On-site or home	On-site or home	On-site				
Informed consent	X											
Inclusion/exclusion criteria	X	X										
Patient demography	X											
Medical/surgical history	X											
Prior/concomitant medications	X	X	X	X	X	X	X	X	X	X	X	X
Randomization		X										
Study treatment administration^c												
Training injection with both devices (prior to randomization) ^d		X										
alirocumab SC injection using SYDNEY		X ^e				X ^f	X ^f	X ^e				
alirocumab SC injection using AI		X ^e										
Dispense/Complete/Review patient diary		X				X ^f	X ^f	X				
Contact IRT		X				X	X	X				X
Dispense alirocumab device		X				X ^f	X ^f	X				
Collect devices post-injection		X					X	X				
Treatment compliance		X					X	X ^g				
End user data recording												
Product Technical Complaints		X				X ^f	X ^f	X				
Patient perspective questionnaire ^h								X				
Injection-Treatment Acceptance Questionnaire (I-TAQ®) ⁱ								X				
Injection Experience questionnaire ^j		X				X	X	X				

Phase	Screening	Treatment Phase										
Day ^a	D-14 to D-1	D1	D8 (±1)	D15 (±1)	D22 (±1)	D29 (±3)	D57 (±3)	D85 (±3) EOT	D92 (±1)	D99 (±1)	D106 (±1)	D113 (±3) EOS
Week	Wk-2 to Wk 0	Wk 0	Wk 1	Wk 2	Wk 3	Wk 4	Wk 8	Wk 12	Wk 13	Wk 14	Wk 15	Wk 16
Visit (visit number)	1	2	3 ^b	4 ^b	5 ^b	6 ^b	7 ^b	8	9 ^b	10 ^b	11 ^b	12
Place where visits may occur	On-site	On-site	On-site or home	On-site	On-site or home	On-site or home	On-site or home	On-site				
Safety												
Physical examination	X											X
Height	X											
Body weight	X											X
Vital signs (Blood Pressure ^k , Heart Rate)	X	X				X	X	X				X
Hematology ^m , biochemistry ^m (including fasting plasma glucose)	X	X										X
Creatine phosphokinase	X	X				X	X	X				X
Liver function panel (ALT, AST, ALP & total bilirubin ^l)	X	X				X	X	X				X
Serum pregnancy test (if applicable)	X											
Urine pregnancy test (if applicable)		X										X
Adverse event collection	X	X	X	X	X	X	X	X	X	X	X	X
Pharmacokinetics												
alirocumab pharmacokinetic samples ⁿ		X	X	X	X	X	X	X	X	X	X	X
ADA		X ^o				X ^o						X
Pharmacodynamics /efficacy												
Lipid parameters (LDL-C, total-C, HDL-C, triglyceride)	X	X ^o				X ^o	X ^o	X ^o				X

Abbreviations: EOT: end-of-treatment, EOS: end-of-study, SC: subcutaneous, IRT: Interactive response technology, ADA: anti (alirocumab) - drug antibody, ALT: Alanine aminotransferase, AST: Aspartate aminotransferase, ALP: Alkaline phosphatase, LDL-C: Low density lipoprotein cholesterol, total-C: Total cholesterol, HDL-C: High density lipoprotein cholesterol, AI: Autoinjector, PCSK9: Proprotein convertase subtilisin/kexin type 9, γGT: gamma-glutamyl transferase.

a Day is expressed in reference to the 1st administration of alirocumab (D1).

b Visits 3, 4, 5, 6, 7, 9, 10 and 11: PK sample to be collected, these visits can be either done on site or be home-visits.

c The self-administration on Day 1 only will be done under supervision (guidance provided) on site. Self-administrations on Week 4 (Day 29) and Week 8 (Day 57) will be done at home or on site, unsupervised and without any guidance. The self-administration on Week 12 (Day 85) will be done at the site and will be observed (no guidance provided, considered unsupervised). Injection site will be documented.

d Patients will first receive paper-based training with each device by the site. They will then practice one injection with each device (SYDNEY and AI) into a training pad.

- e Self-injection at the site on Days 1 (supervised) and 85 (observed, considered unsupervised). Device collected immediately after dosing.
- f Self-injection at home or on-site: If self –injection is performed at home, a visiting Nurse will bring supplies for blood draw, diary, and dispensed IMP kit to subject's home and collect IMP materials post injection. The Visiting Nurse will not observe or provide guidance and therefore the injection will be unsupervised. After the completion of the visit the Visiting Nurse will collect all study supplies and return them to the site.
- g Treatment compliance at Week 12 applies for injection done at Week 8 and injection done at Week 12.
- h Patient perspective questionnaire: Completed by the patient after the last injection to record patient experience and satisfaction associated with use of SYDNEY to administer the 300 mg dose.
- i Injection-Treatment Acceptance Questionnaire (I-TAQ®): Completed by the patient after the last injection, to measure their acceptance of self-injection treatment.
- j Injection Experience questionnaire: Completed by the patient after each self-injection (AI or SYDNEY) addressing specific aspects of using the device.
- k Blood pressure after 5 minutes in seating resting position.
- l Total bilirubin (and, in case of values above the normal range, differentiation in conjugated and non-conjugated bilirubin).
- m Hematology includes: red blood cell count, hematocrit, hemoglobin, white blood cell count with differential count (neutrophils, eosinophils, basophils, monocytes, and lymphocytes), and platelets. Biochemistry includes: sodium, potassium, chloride, plasma glucose, calcium, urea nitrogen, creatinine, total proteins, albumin, γ GT.
- n When alirocumab is to be administered, PK samples will be taken prior to alirocumab injection (Includes assay of total and free PCSK9).
- o Prior to dosing with any IMP.

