8.1.3 Timing of administration

On Day 1, prior to the randomization, all patients will be trained in self-injection using both devices at clinical site. They will first receive paper-based training with each device by the investigator or designee. They will then practice one injection with each device (current and new auto-injector devices) into a training pad.

Randomization will occur when training is completed and considered satisfactory by the investigator or designee.

Patients will be randomized to receive self-administered alirocumab 300 mg Q4W subcutaneously via either SYDNEY or AI for the first injection on Week 0 (Day 1).

The treatment period will start as soon as possible after the call for randomization using the treatment kit number provided by the Interactive Response Technology (IRT). The first injection after randomization will be done at the investigational site by the patient under direct site staff supervision. Patients will be monitored at the investigational site for at least 30 minutes after this first injection.

Subsequently, all patients will receive self-administered alirocumab 300 mg Q4W via SYDNEY for the 2nd, 3rd and 4th injections on Week 4 (Day 29), Week 8 (Day 57) and Week 12 (Day 85).

- The 2nd and 3rd injections will be done unsupervised at home or on site.
- The 4th injection will be done on site under observation by a caregiver (considered unsupervised), as no direction or prompting will be given. This observation will assess whether the self-injection is performed adequately with this information recorded in the e-CRF.

IMP should ideally be administered subcutaneously at approximately the same time of the day Q4W; however it is acceptable to have a window period of ± 3 days. The time of the day is based on patient's preference.

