9.2.2.5 Pharmacokinetics parameters

The pharmacokinetic parameters listed in [Table 4](#) will be calculated, using non-compartmental methods for alirocumab serum concentrations after single and multiple doses. The parameters will include, but not be limited to the following.

Table 4 - List of pharmacokinetic parameters and definitions

Parameters	Drug/Analyte	Matrix	Definition/Calculation
C _{max}	SAR236553	Serum	Maximum serum concentration observed
C _{trough}	SAR236553	Serum	Serum concentration observed just before treatment administration during repeated dosing
t _{max}	SAR236553	Serum	Time to reach C _{max}
AUC _{0-tau}	SAR236553	Serum	Area under the serum concentration versus time curve calculated using the trapezoidal method during a dosage interval

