- Dispense patient diary to be completed on site
- Record in the appropriate e-CRF page if the self-injection was performed appropriately with the full injection done
- Review patient diary and record patient complaint (including PTC) in the Patient complaints form, if any reported for this injection (as described in [Section 9.1](#))
- Schedule home-visits or on-site visits according to patient preference for Visit 9 (Week 13), Visit 10 (Week 14), and Visit 11 (Week 15)
- Schedule a visit for Week 16 (Day 113 [\pm 3 day], Visit 12)

10.1.7 Visit 9: Day 92 \pm 1 day, Week 13; Visit 10: Day 99 \pm 1 day, Week 14; Visit 11: Day 106 \pm 1 day, Week 15

These visits may be performed on site or as home-visits.

- Record concomitant medications
- Record AEs (including SAE and AESI)
- Obtain blood samples for:
 - Pharmacokinetics: PK parameters including assay of total and free PCSK9
- Remind patient to be in fasting conditions (ie overnight, at least 10 to 12 hours fast and refrain from smoking) for next study site visit. Also, alcohol consumption within 48 hours and intense physical exercise within 24 hours preceding the next visit are discouraged.

10.1.8 Visit 12 (end-of-study): Day 113 ± 3 days, Week 16

This visit must be performed on site.

The following procedures will be performed:

- Perform a physical examination, including body weight
- Record vital signs including systolic and diastolic blood pressure (measured after 5 minutes in a seated resting position) and heart rate
- Record concomitant medications
- Record AEs (including SAE and AESI)
- Obtain fasting blood samples for:
 - Lipids panel
 - Hematology
 - Biochemistry
 - Liver function panel.
 - CPK
 - Pharmacokinetics: PK parameters including assay of total and free PCSK9
 - Detection of anti-alirocumab antibodies.
- Obtain urine sample for pregnancy test (for WOCBP, only)
- Contact IRT to update the patient's status (study completion).

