2.5.4 Windows for time points

Data analyzed by time point (except PK and PCSK9 variables) will be summarized using the analysis windows given in Table 1. These analysis windows will be applicable for all analyses, and they are defined to provide more homogeneous data for time point-specific analyses. For PK, since measurements are planned every week, e-CRF visits will be used instead of analysis windows.

Table 1 - Analysis windows definition

Time point	Targeted study day	Analysis window in study days
Week 4	29	15 to 42
Week 8	57	43 to 70
Week 12	85	71 to 98
Week 16	113	99 to 126

Study days are calculated from the day of first IMP injection, the day of first open-label IMP injection being Day 1. For randomized but not treated patients, Day 1 is the day of randomization.

If multiple valid values of a variable exist within an analysis window, the nearest from the targeted study day will be selected. If the difference is a tie, the value after the targeted study day will be used. If multiple valid values of a variable exist within a same day, then the first value of the day will be selected when time is available, else the scheduled visit will be selected.

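### PK visits after the last dose are counted from Day 1, not from the Week 12 injection, so their ±1 day windows do not control post-dose time

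*Protocol*

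**What the plan says.** - **Anchor.** Footnote a of the flow chart (Protocol 1.2) reads "Day is expressed in reference to the 1st administration of alirocumab (D1" and applies to every visit.
- **Last injection.** The flow chart puts Week 12 at Day 85 ±3. Protocol 8.1.3 says of injection timing generally: "however it is acceptable to have a window period of ± 3 days".
- **Samples after it.** Visits 9, 10 and 11 are at Day 92, 99 and 106, each ±1 (Protocol 10.1.7). The last is "Visit 12 (end-of-study): Day 113 ± 3 days, Week 16" (10.1.8). The Week 12 sample itself is pre-dose: "When alirocumab is to be administered, PK samples will be taken prior to alirocumab injection" (flow chart, footnote n).
- **Booking.** On the day of the last injection, Protocol 10.1.6 tells the site: "Schedule home-visits or on-site visits according to patient preference for Visit 9 (Week 13), Visit 10 (Week 14), and Visit 11 (Week 15". It then books Week 16 at Day 113 ±3. Neither instruction refers to the date of the injection just given.
- **Use of the data.** "Alirocumab PK parameters after the first and the last dosing" is a listed secondary endpoint (protocol synopsis and 9.2.2), and PK until Week 16 is a secondary objective. Table 4 defines AUC0-tau as "Area under the serum concentration versus time curve calculated using the trapezoidal method during a dosage interval" and Ctrough as a pre-dose concentration.
- **SAP.** Section 2.5.4 says: "For PK, since measurements are planned every week, e-CRF visits will be used instead of analysis windows". Section 2.4.4.2.2 summarises single-arm PK for all patients together.

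**The concern.** A ±1 day window on a PK visit is there to hold time since dose nearly constant. After the first dose it does, because Day 1 is the dose day. After the last dose, the visit window and the ±3 day injection window are separate and their widths add up.

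Only four samples follow the last dose, so the time of the Week 13 sample largely determines observed Cmax and tmax. The Week 16 sample closes the dosing interval. If post-dose time varies with scheduling, these parameters carry patient-to-patient variation that comes from the calendar and not from the drug or the device.

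**Working it through.** **1. The plan's own days.** Nominal day = 7 × week + 1 gives 85, 92, 99, 106 and 113 for Weeks 12 to 16. These match the flow chart and lie 7, 14, 21 and 28 days after a Day 85 dose.

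**2. Permitted time since the last dose.** Shortest = earliest visit day − 88. Longest = latest visit day − 82. For comparison, the first-dose column uses Day 8, 15 and 22 (±1) and Day 29 (±3), minus Day 1.

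| Visit | Days after last dose | Days after first dose (matching visit) |
|---|---|---|
| Week 13 | 91−88 to 93−82 = 3 to 11 | 6 to 8 |
| Week 14 | 98−88 to 100−82 = 10 to 18 | 13 to 15 |
| Week 15 | 105−88 to 107−82 = 17 to 25 | 20 to 22 |
| Week 16 | 110−88 to 116−82 = 22 to 34 | 25 to 31 |

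Counting the same windows from the actual Week 12 injection gives exactly the first-dose column. Under the current rule, adjacent ranges overlap: one patient's Week 13 sample (11 days) can be later after dosing than another's Week 14 sample (10 days).

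**3. Typical spread.** Assume dose day and visit day are independent and uniform over whole days in their windows. A window of n days has variance (n² − 1)/12.

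- Dose window, 7 days: variance 4. Visit window, 3 days: variance 0.667.
- Week 13 now: SD = √(4 + 0.667) = 2.2 days. Counted from the injection: √0.667 = 0.8 days.
- Week 16 now: SD = √(4 + 4) = 2.8 days. Counted from the injection: √4 = 2.0 days.
- Of the 21 possible dose/visit day pairs for Week 13, 12 (57%) fall outside 6-8 days. Of the 49 for Week 16, 12 (24%) fall outside 25-31 days.

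**4. Effect on the parameters.** The documents give no half-life or tmax, so these are assumptions: one compartment, half-life 7 to 20 days, tmax 4 to 7 days, doses on Day 1, 29, 57 and L (82 to 88), and AUC by linear trapezoid with actual times to the last sample. Concentration is the sum over doses d of ka/(ka − ke) × [exp(−ke(t − d)) − exp(−ka(t − d))]. Here ke = ln 2/half-life, and ka solves ln(ka/ke)/(ka − ke) = tmax. Every in-window combination is weighted equally, and results are relative to a Day 85 dose with nominal visits.

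| Quantity | Counted from Day 1 | Counted from Week 12 injection |
|---|---|---|
| Week 16 concentration, log-SD, half-life 7 days | 0.27 | 0.20 |
| Week 16 concentration, log-SD, half-life 20 days | 0.08 | 0.07 |
| Week 16 concentration, extremes, half-life 7 days | 0.56 to 1.78 | 0.73 to 1.37 |
| Week 16 concentration, extremes, half-life 20 days | 0.84 to 1.19 | 0.87 to 1.15 |
| Observed Cmax, log-SD, worst case | 0.14 | 0.06 |
| AUC, log-SD, range over assumptions | 0.04 to 0.076 | 0.043 to 0.059 |

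The worst case for Cmax is half-life 7 days with tmax 4 days. At half-life 20 days with tmax 7 days, the Cmax log-SD is about 0.03 either way. Observed tmax runs from 3 to 12 days now, against 6 to 8 days if counted from the injection. Under the current rule, geometric means move by less than 1% for the Week 16 concentration, about 1% for AUC and at most about 4% for Cmax.

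**The case against.** The case for leaving the plan alone has several sound parts.

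- **The device comparison is safe.** The only PK estimates with confidence intervals are the SYDNEY/AI ratios after the first dose, where Day 1 is the dose day. A reader might infer that the bridging comparison is compromised; it is not. No first-versus-last-dose comparison is planned either.
- **The extremes exaggerate.** A range of 0.56 to 1.78 needs opposite ends of two windows and the shortest assumed half-life. Week 16 keeps its own ±3 days under any anchor, so part of the spread would remain.
- **The Week 16 sample is not called a trough.** Table 4 defines Ctrough as pre-dose and no dose follows Week 16, so the documents do not support saying that Ctrough varies by that factor. They leave the last-dose Ctrough undefined.
- **SAP 2.5.4 does not put nominal times into the parameters.** It governs summaries by time point. Neither document says which times enter the non-compartmental calculation. Administration and visit dates are source data (Protocol 10.2), so actual days can be recovered.
- **Truncated AUC is not prescribed.** A patient dosed on Day 88 and seen on Day 110 has 22 of 28 days observed, but nothing says AUC0-tau stops there.

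All of this limits the harm. It does not change the day ranges, and no section links Visits 9 to 12 to the last injection. Actual times would correct tmax and AUC for the shifted sampling, but could not recover a peak that was not sampled.

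**Conclusion.** The point holds as a design inefficiency of modest size. The day ranges follow directly from the flow chart and need no assumption. The consequence is mainly added scatter, clearest for tmax, for Cmax at the shorter assumed half-life and for the Week 16 concentration. AUC changes little and not always in the same direction.

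The sizes rest on the one-compartment model, half-life 7 to 20 days, tmax 4 to 7 days and uniform use of the windows. If sites keep close to nominal days the scatter is smaller. At a 20-day half-life the gain from re-anchoring is slight for the Week 16 concentration (log-SD 0.08 to 0.07). The endpoint affected is secondary, pooled and descriptive, and neither the primary endpoint nor the first-dose PK ratios are touched. The change is worth making because it is cheap.

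**What to change.** **Protocol.** In the flow chart and sections 10.1.6 to 10.1.8, set Visits 9, 10 and 11 at 7, 14 and 21 days (±1), and Visit 12 at 28 days (±3), after the actual Week 12 injection. The injection window is unchanged. These visits are already scheduled at Visit 8, when the date is known. Visit 12 would fall between Day 82 + 25 = 107 and Day 88 + 31 = 119, inside the SAP Week 16 window of Day 99 to 126, so lipid and safety time points are kept.

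**SAP.** State that PK parameters use actual time since the most recent injection, that AUC0-tau is computed to 28 days, and which sample gives the last-dose Ctrough. Do not add a rule excluding Week 16 values by post-dose day; it would discard data for little gain.

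**Cost.** No extra visit, sample or patient. It needs a protocol amendment with ethics approval before implementation (Protocol section 15), and the target end-of-study date can move by up to 3 days. If the visits cannot be moved, the SAP wording alone still removes much of the ambiguity.
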